H5. There will also be a reduced bias towards sad emotional expressions (i.e. greater threshold change in favour of happy) following acute alcohol consumption compared to placebo (happy-sad 2AFC task).

Study Design

This is a placebo-controlled experimental study, which comprises one within-subjects factor of drink (0.4 g/kg alcohol, placebo) and one between-subjects factor of trait

anger (high, low). For the 6AFC task (see Measures and Materials), there will be an additional within-subjects factor of emotion (happy, sad, angry, disgust, surprise and fear). The primary dependent measures will be hit rate and false alarms (6AFC task) and threshold response (2AFC tasks). We will also take subjective measures of state aggression, mood and intoxication. For these outcomes, there will be an additional within-subjects factor of time (pre-consumption, post-consumption).

Study Site

School of Experimental Psychology, [name], Bristol University, [name].

Participants and Recruitment

Male and female social alcohol drinkers (n = 88; 50% male) will be recruited from the staff and students at the University of Bristol, and the general population. Participants will attend two sessions of approximately 75 minutes each. Participants will be recruited by existing email lists, poster and flyer advertisements, and by word of mouth. They will be asked to contact the researcher for further details of the study if they are interested in taking part. Those who meet the initial study inclusion criteria will be asked to complete a short online screening questionnaire. Participants that are eligible will be sent the information sheet, and asked to contact the researcher again if they would like to sign up for the study or if they require further information. Participants will be required to not drink alcohol 24 hours prior to the study session. On completion of the study, participants from the general population will be reimbursed £20 or equivalent course credits (if eligible).

Inclusion criteria

- Good physical and psychiatric health (self-report)
- Drinks between 5 and 35 alcoholic units* per week if female or between 10 and 50 alcoholic units* per week if male
- Aged between 18 and 40 years
- Be high or low in trait aggression, defined by a score above 41 and below 32 on the Anger Expression Index subscale of the State-Trait Anger Expression Inventory-2 (STAXI-2), respectively.
- Speaks English as first language or equivalent level of fluency

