- Able to attend two sessions, at least one week apart

* One unit equals one 25 ml single measure of spirit (ABV 40%), or a third of a pint of beer (ABV 5-6%) or half a standard (175 ml) glass of red wine (ABV 12%).

Exclusion criteria

- Alcohol consumption less than 24 hours prior to the study sessions
- Weight less than 50 kg if female or 60 kg if male
- Strong familial history of alcoholism defined as one or more immediate relative (parent, sibling) or more than one other relative (e.g., cousin, grandparent) (self-report)
- History of psychiatric disorder (including drug addiction) (self-report)

- Uncorrected visual impairment
- Uncorrected auditory impairment

Sample size determination

A sample size calculation based on previous findings from a study using a between-subjects design (Craig et al., 2009) indicates an effect size of $d = 1.0$ for the difference between alcohol and placebo on sadness recognition ($M = 0.14$, $SD = 0.02$; $M = 0.12$, $SD = 0.02$, respectively). These data indicate that we require a total sample size of 46 participants to achieve 90% power at an alpha level of 5%. As we are including a between-subjects factor, we plan to recruit sufficient numbers in each group to achieve this level of power to observe a main effect of alcohol. However, as this is likely to be an inflated effect size, we used a more conservative effect size estimate of $d = 0.7$. Based on this estimate, 88 participants would be required in each drink condition in a between-subjects design to achieve 90% power at an alpha level of 5%. However, as our alcohol/placebo condition will be within-subjects, we consider this a conservative estimate for our study, as we are using a within-subject design that will be less subject to less individual variation. We will recruit 44 participants per trait group (total $n = 88$). This would achieve 90% to detect an effect size of $d_z = 0.5$ (alcohol vs. placebo) within each trait group. Interaction analyses will be exploratory.

Withdrawal of participants

Participants will be informed that they can withdraw from the study at any time. If participants withdraw from the study due to an adverse event or reaction, they will receive full reimbursement (£20 or equivalent course credits). For all other withdrawals (i.e., not related to an adverse event or reaction), participants will be reimbursed an amount commensurate with the time spent in the laboratory.

Randomisation

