In addition, a happy-angry and a happy-sad two-alternative forced choice task (2AFC) will also be run. For each of these tasks, a 15-image morph sequence has been created, which runs from one full emotional exemplar to another (i.e., unambiguously happy to unambiguously angry / unambiguously happy to unambiguously sad). The full exemplar images are used as endpoints to create a linear morph sequence of emotionally ambiguous images that change incrementally from happy to angry in one task version and happy to sad in the other. On each trial of the happy-angry 2AFC task, a frame from this morph continuum is presented for 150 ms (backward masked), and participants are required to identify whether the emotion in the face is happiness or anger, by pressing designated keys on the keyboard. On each trial of the happy-sad 2AFC task, a frame from this morph continuum is presented for 150 ms (backward masked), and participants are required to identify whether the emotion in the face is happiness or sadness. Each image is presented three times, giving 45 trials in total for each 2AFC task.

Questionnaires: Trait aggression will be measured using the anger expression index subscale (AXi) of the State-Trait Anger Expression Inventory (STAXI-2) (Spielberger, 1999). This is a widely-used measure of aggression that has been validated on a variety of normal and clinical samples (Forgays, Forgays, & Spielberger, 1997). Normative data for the STAXI-2 scale are based on samples of normal adults (n=1,644) ranging from 16-63 years old; these data shows a mean score of 32.9 (SD = 13.4) for the AXi subscale. High and low trait groups will be defined by a score above the 60th percentile and below the 40th percentile on this subscale, respectively.

Other questionnaire measures will include the State Anger Subscale (S-Ang) of the STAXI-2 (Spielberger, 1999), Positive and Negative Affect Schedule (PANAS) (Watson, Clark, & Tellegen, 1988), Biphasic Alcohol Effects Scale (BAES) (Martin, Earleywine, Musty, Perrine, & Swift, 1993) and Alcohol Use Disorders Identification Test (AUDIT) (Saunders, Aasland, Babor, Delafuente, & Grant, 1993).

Procedure

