Prior to testing, participants will complete the STAXI-2 online. Only individuals that meet the high/low trait anger inclusion criteria will be invited to participate. On arrival at the first session, participants will be given the opportunity to read the information sheet again and ask questions, before providing written informed consent. The researcher will conduct a short screening procedure to verify eligibility, which includes taking measures of weight and breath alcohol concentration (BrAC) (only participants with a BrAC of zero will be enrolled). Study documentation from failed screenings will be destroyed using the School's confidential waste facility. If eligible, participants will complete questionnaire measures (AUDIT, PANAS, BAES, S-Ang).

Participants will attend two sessions (order counterbalanced): at one session they will consume an alcoholic drink and at the other they will consume a matched placebo drink (see Drug Administration section for more details). Testing sessions will be held at least one week apart. Participants will be given 10 minutes to consume all of their drink and a further 10 minutes to sit quietly to allow for absorption. After drink consumption, participants will complete the 6AFC and 2AFC tasks. They will then complete questionnaire measures (PANAS, BAES, S-Ang), and a BrAC reading. Before leaving the session, participants will be required to read and sign a safety card, be offered the opportunity to stay behind until they feel any effects of alcohol have worn off and be offered a taxi home. At the end of session two, participants will be debriefed and reimbursed.

Table 1: Testing procedure timeline

Time (min)	Activity/Task
0	Informed consent and screening (session one only)
10	Questionnaire measures (AUDIT, PANAS, BAES, S-Ang)
20	Drink administration
30	Alcohol absorption period
40	Computerised tasks
65	Questionnaire measures (PANAS, BAES, S-Ang), BrAC reading
75	Debrief and reimbursement (session two only).

Drug Administration

The alcoholic drink will be 0.4 g/kg alcohol (vodka) with one part vodka and three parts tonic water. The placebo drink will comprise the same volume of tonic. Drinks will be flavoured with lime cordial and chilled prior to serving. The rim of the glass will be sprayed with a vodka mist. Drinks will be served double blind and will be made at the start of each session by a research collaborator.

Statistical Plan

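### The AXi cut-offs for high and low trait aggression (above 41, below 32) are not the 60th and 40th percentiles under the only norms the protocol gives

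*Protocol*

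**What the plan says.** Two sections of the protocol define the trait groups on the same scale, the Anger Expression Index (AXi) of the STAXI-2.

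- **Participants and Recruitment, Inclusion criteria.** High and low trait aggression are "defined by a score above 41 and below 32 on the Anger Expression Index subscale", in that order.
- **Measures and Materials, Questionnaires.** "High and low trait groups will be defined by a score above the 60th percentile and below the 40th percentile on this subscale, respectively".

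The sentence before the percentile definition supplies the only norms in the protocol: "Normative data for the STAXI-2 scale are based on samples of normal adults (n=1,644) ranging from 16-63 years old", and "these data shows a mean score of 32.9 (SD = 13.4) for the AXi subscale". No other reference population, no age- or sex-specific norm and no conversion from percentile to raw score is given.

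The Procedure section makes the rule a gate: "Only individuals that meet the high/low trait anger inclusion criteria will be invited to participate". Sample size determination sets the target by group: "We will recruit 44 participants per trait group".

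**The concern.** If 41 and 32 were the 60th and 40th percentiles, they should lie at similar distances either side of the centre of any roughly symmetric score distribution. They do not. The upper cut-off is 8.1 points above the norm mean and the lower is 0.9 points below it.

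Trait group is the only between-subjects factor. It decides who may enrol and it enters every main ANOVA. If the score rule and the percentile rule pick out different people, the report may describe the groups as the upper and lower 40% of the norm when they are not, and someone who replicates the study from the percentile sentence would enrol a different sample. The protocol also has the records of ineligible people destroyed after screening, so anyone turned away under the wrong rule could not be recovered later.

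**Working it through.** **Inputs from the protocol.** Cut-offs 41 and 32 (Inclusion criteria); 60th and 40th percentiles, norm mean 32.9 and SD 13.4 (Questionnaires). The shape of the AXi distribution is not given. I assume normal as the base case and vary it below.

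**Step 1. Try to reproduce the cut-offs.** Percentile score = mean + z × SD, with z = ±0.2533 for the 60th and 40th percentiles.

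- 60th: 32.9 + 0.2533 × 13.4 = 36.3. The protocol has 41, which is 4.7 points higher.
- 40th: 32.9 − 0.2533 × 13.4 = 29.5. The protocol has 32, which is 2.5 points higher.

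**Step 2. Run it backwards.** Percentile = Φ((cut-off − 32.9) / 13.4).

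- 41: Φ(8.1 / 13.4) = Φ(0.604) = 72.7%.
- 32: Φ(−0.9 / 13.4) = Φ(−0.067) = 47.3%.

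A normal distribution with 41 and 32 as its 60th and 40th percentiles would need a mean of (41 + 32) / 2 = 36.5 and an SD of 4.5 / 0.2533 = 17.8, against the stated 32.9 and 13.4.

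**Step 3. Vary the shape, holding mean 32.9 and SD 13.4.**

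| Assumed shape | 40th | 60th | Percentile of 32 | Percentile of 41 |
|---|---|---|---|---|
| Normal | 29.5 | 36.3 | 47.3% | 72.7% |
| Logistic | 29.9 | 35.9 | 47.0% | 75.0% |
| Uniform | 28.3 | 37.5 | 48.1% | 67.4% |
| Gamma | 27.9 | 34.5 | 52.7% | 75.6% |
| Lognormal | 27.6 | 33.6 | 55.0% | 77.6% |
| Beta on an assumed 0-96 range | 28.4 | 35.6 | 50.2% | 73.1% |
| Pearson III, skew −1 | 31.7 | 38.2 | 40.8% | 69.4% |
| Pearson III, skew −2 | 34.0 | 39.5 | 34.4% | 67.3% |
| Pearson III, skew −3 | 35.9 | 39.7 | 28.6% | 72.9% |

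None of these shapes puts the 60th percentile at 41. The lower cut-off is nearly met at skew −1.

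**Step 4. Who is treated differently (normal case).** Everyone above 41 is also above 36.3, and everyone below 29.5 is also below 32, so the rules are nested.

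- High by percentile but not by score (36.3 to 41): 72.7% − 60% = 12.7%.
- Low by score but not by percentile (29.5 to 32): 47.3% − 40% = 7.3%.

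The score rule takes the top 100% − 72.7% = 27.3% and the bottom 47.3%. Allowing for whole-number scores (42 or more, 31 or less, with continuity correction), the shares are 26.1% and 45.8%.

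**Step 5. Does the score rule weaken the contrast?** Mean AXi in the high group minus the mean in the low group:

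| Shape | Score rule | Percentile rule |
|---|---|---|
| Normal | 49.2 − 21.6 = 27.6 | 45.8 − 20.0 = 25.9 |
| Gamma | 28.5 | 25.3 |
| Lognormal | 28.8 | 24.3 |

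(Differences are taken before rounding.) The score rule separates the groups slightly more, not less.

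**Step 6. Sample size.** A paired t-test with a standardised difference of 0.5 and 44 participants has 90.0% power at two-sided 5%, as the protocol states for each trait group. The definition of the groups does not enter that calculation.

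**The case against.** The best defence is that the operating rule is not really in doubt. The exact scores stand under the inclusion criteria, and the Procedure section refers back to those criteria. The percentile sentence contains no score and could not be applied at screening without a table. Read this way, the defect is an inaccurate description and not two competing entry rules. Much of that stands, and it is a reason to rate the point below must-fix. It does not remove the conflict: the percentile sentence says how the groups will be defined, and it directly follows norms that do not yield 41 and 32.

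A second defence is that only the norm table can settle the matter. This is also fair. A mean and an SD do not make 32 and 41 impossible as the 40th and 60th percentiles. On an assumed integer range of 0 to 96, a linear-programme check finds distributions with this mean and SD, 40% of scores at 31 or below and 40% at 42 or above, with skewness of either sign. A reader might infer that the percentiles could be right only under left skew; that is not so. Such distributions are unusual, however, and the protocol names neither one of them nor a subgroup table that would explain the cut-offs.

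Two further inferences are tempting and unsupported. One is that the score cut-offs dilute the high/low contrast; step 5 shows the opposite under the three shapes tried. The low group reaches almost to the norm mean, but its own average is 21.6 in the normal case, (32.9 − 21.6) / 13.4 = 0.84 SD below that mean. The other is that a fifth of those screened would be reclassified. The 12.7% and 7.3% are shares of an assumed normal norm population. The volunteers are drinkers aged 18 to 40, and their score distribution is not given.

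**Conclusion.** The mismatch holds as an internal inconsistency in how the trait groups are defined. Under the stated norms and a normal approximation, 41 and 32 are near the 73rd and 47th percentiles (gamma: 76th and 53rd), not the 60th and 40th. The upper cut-off is the firm part, since no shape tried reproduces it. The lower gap is smaller and depends on shape. An unstated norm table or an unusual distribution cannot be excluded.

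The consequence is asymmetric groups that the percentile sentence misdescribes, or a different intake at the margins if that sentence were used to screen. A reader might take this as a threat to the main results. The protocol does not support that: H1 to H5 all compare alcohol with placebo within participants, interaction analyses are declared exploratory, and the sample size is unaffected. Severity is moderate. The documents do not show which definition was intended.

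**What to change.** Before screening starts, check 41 and 32 against the norm table and name the reference population from which the percentiles are read. Then state one rule, in the same terms, in the Inclusion criteria and in the Questionnaires section, and use it in the online screening. If 41 and 32 are kept, replace the 60th/40th percentile statement with the percentiles read from that table. The normal-approximation values above show the mismatch and should not be copied into the protocol. If the percentile rule is kept, take the raw scores from the same table.

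The cost is one look-up and matching wording in two sections. No participants, visits or procedures are added.

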Ethics approval has been obtained from the Faculty of Science Research Ethics Committee at the University of Bristol (approval code: 26011747361). The study will be conducted according to the revised Declaration of Helsinki (2013) and the 1996 ICH Guidelines for Good Clinical Practice E6(R1). The investigator will explain the nature, purpose and risks of the study to the participant. The participant will receive the information sheet in advance of the study session. There will be no time restriction on how long participants take to respond, with the exception that participants who respond after all study places have been filled will not be offered a place on the study. Therefore, participants will be given sufficient time to read the information, consider any implications, and raise any questions with the investigators prior to making a decision to participate. On arrival at the study session participants will be given the opportunity to read the information sheet again and ask the investigator questions. Written consent will then be obtained. Participants will be informed that they are free to withdraw at any time.

Safety

Participants will be administered alcohol during one of the sessions. The dose will be 0.4 g/kg of body weight up to 90 kg. Participants weighing more than 90 kg will receive a dose based on 90 kg. This dosing will administer drinks ranging between around 2.5 to 4.5 units of alcohol (for weight ranges between 50-90 kg). We expect that at this dose, participants will feel some effects of alcohol but we do not expect high levels of intoxication (all participants will be weekly alcohol consumers). However, to ensure the safety of our participants, they will know in advance of the study that they may receive this dose of alcohol, and therefore will be able to make any necessary arrangements. They will be advised that should stay behind until they feel the effects of alcohol have worn off and they shouldn't drive, operate heavy machinery or do anything that would be considered unsafe after drinking alcohol for the rest of the day. Participants who have received alcohol will be asked to read and sign a post-study safety form to confirm that they understand these risks. We have standard operating procedures in place for adverse effects of alcohol (i.e., nausea, intoxication) and have facilities for people to stay behind until they feel ready to leave. Participants will be offered a local taxi at the end of the session.

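### The eligibility lists have no criterion on pregnancy, breastfeeding, interacting medicines or recent non-addicted drug use, and participants given alcohol at session two have no eligibility check scheduled that day

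*Protocol*

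**What the plan says.** **Who is enrolled.** Participants and Recruitment plans "Male and female social alcohol drinkers (n = 88; 50% male". The inclusion list requires "Aged between 18 and 40 years", "Good physical and psychiatric health (self-report" and, for women, "Drinks between 5 and 35 alcoholic units* per week if female".

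**Who is excluded.** The exclusion list has six items: recent alcohol, low body weight, a strong family history of alcoholism, psychiatric history, uncorrected visual impairment and uncorrected auditory impairment. The two that concern substances are "Alcohol consumption less than 24 hours prior to the study sessions" and "History of psychiatric disorder (including drug addiction) (self-report".

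**When eligibility is checked.** Under Procedure, the researcher verifies eligibility on arrival at the first session; weight and breath alcohol (BrAC) are the measures named. Table 1 agrees: "Informed consent and screening (session one only". The only other BrAC reading in Table 1 is at 65 minutes, after the drink (20 minutes) and the computerised tasks (40 minutes).

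**The safety argument.** The Safety section caps the dose at the amount for 90 kg and says "we do not expect high levels of intoxication (all participants will be weekly alcohol consumers". It adds advance notice of the dose, advice on driving and similar activities, a signed form, the option to stay on site and a taxi.

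**The concern.** This study gives alcohol to volunteers for experimental purposes, so eligibility is the main protection before the drink is served. The lists are itemised, and the on-site check exists to verify them. A person whom no item covers can truthfully pass every item.

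Two things are at stake. First, someone who is pregnant or breastfeeding, or who has taken a medicine or drug that interacts with alcohol, could be given the study drink although the protocol's safety reasoning does not consider that situation. Second, the protocol sets a rule for both sessions but schedules the means of checking it at only one. For half the sample, the unchecked session is the one with alcohol.

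**Working it through.** No stated figure is in dispute. The check sets the sections against each other, with simple arithmetic for the numbers exposed.

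**Inputs**
- n = 88, half male (Participants and Recruitment).
- Equal numbers in each session order (Randomisation).
- Dose 0.4 g/kg, with body weight capped at 90 kg (Drug Administration; Safety).
- Sessions at least one week apart, with no maximum gap stated (Inclusion criteria; Procedure).

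**Exposure**
- Women: 0.50 × 88 = 44, all aged 18 to 40.
- Alcohol per person: 0.4 × 50 kg = 20 g; 0.4 × 90 kg = 36 g.
- The Safety section gives this range as about 2.5 to 4.5 units. Then 20 / 2.5 = 8 g per unit and 36 / 4.5 = 8 g per unit, so the stated range is internally consistent.
- Alcohol at session two: 88 / 2 = 44 participants.

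**Does any existing item cover the four situations?**

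| Item | Pregnancy or breastfeeding | Interacting medicine | Recent non-addicted drug use |
|---|---|---|---|
| Good health by self-report | No; a healthy pregnant or breastfeeding woman can say yes | Partly; may remove people treated for illness, but not someone taking, say, a sedating antihistamine | No |
| Minimum weekly drinking | Partly; a woman abstaining because of a known pregnancy or breastfeeding fails it, but an unrecognised pregnancy does not | No | No |
| Psychiatric history including drug addiction | No | No | No; it covers a disorder, not occasional use |
| 24-hour rule and BrAC | No; alcohol only | No | No |

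**Does the Safety section cover them?** Its expectation of limited intoxication rests on the size of the dose and on habitual drinking. Neither speaks to pregnancy, breastfeeding or a combination with another substance. Advance notice leaves the judgement to the participant, and the remaining measures act after the drink.

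**Session two**
1. The 24-hour exclusion is worded for sessions in the plural, so it applies at both.
2. The eligibility check and the pre-drink BrAC are scheduled at session one only.
3. For the 44 who drink alcohol at session two, the only BrAC scheduled that day follows the study drink, so it cannot show whether they arrived with alcohol already in the body.
4. Their last scheduled eligibility check was at least a week earlier. Any change in between, whether in a listed item or in one of the missing ones, has no scheduled point at which it would be picked up.

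**The case against.** The strongest reply is that this is silence in a partly visible record. The online screening questionnaire and the information sheet are not reproduced, and the on-site screening is described as including weight and BrAC, which is not an exhaustive list. Ethics approval was obtained, and procedures for adverse effects of alcohol are in place. The questions may well be asked in practice.

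Much of that stands. A reader might infer that such people would in fact be enrolled and given alcohol, and the documents do not support so firm a statement. They show only that no listed criterion would turn these people away. The weekly-drinking requirement also matters: it removes many women who know they are pregnant or who avoid alcohol while breastfeeding.

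It does not dispose of the point. Screening verifies eligibility, and a screener question without a matching criterion gives the researcher no stated ground for exclusion. Eligibility belongs in the protocol and is not something a statistical analysis plan would normally supply.

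It can also be said that the 24-hour rule already reaches session two. It does, and that is why the rule and Table 1 need reconciling.

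**Conclusion.** The point holds as a gap in the listed criteria and as a mismatch between the 24-hour exclusion and the screening schedule. About 44 women aged 18 to 40 are planned with no pregnancy or breastfeeding criterion. All 88 participants receive alcohol with no criterion on interacting medicines or recent non-addicted drug use. About 44 take alcohol at session two with no eligibility check scheduled that day. These counts assume full recruitment at the planned sex split and equal order groups. They are numbers within reach of the gap, not numbers harmed; the protocol gives no prevalence from which to estimate the latter.

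Two stronger readings are tempting and should be resisted.
- A reader might infer that nobody is screened for drugs at all. That is wrong, since a history of drug addiction is an exclusion.
- A reader might infer that medicine or drug use threatens the within-person comparison behind H1 to H5. The documents contain nothing on how such substances affect these face tasks and no figure from which to size an effect. Session order is randomised and balanced, so sporadic use unrelated to the assigned drink would not favour either condition. The case rests on participant safety, not on the analysis.

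**What to change.** 1. Add self-report eligibility items covering pregnancy and breastfeeding, and current medicine or drug use. The sponsor should set their clinical content and any time windows; none is proposed here. If the screener already asks these questions, write the corresponding criteria into the protocol.
2. Reconcile Table 1 and Procedure with the 24-hour exclusion by scheduling the brief eligibility questions and a BrAC check before the drink at both sessions.

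The cost is a protocol amendment, a couple of screener questions and about a minute of questions per session, plus one extra breath test at session two. The downside is a few more screen failures or rescheduled sessions. The dose, crossover design, sample size and analysis stay as they are.

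### The recent-drinking exclusion covers both sessions, but the only breath alcohol reading before the drink is taken at session one, so half the planned sessions have no objective check on arrival

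*Protocol*

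**What the plan says.** The Exclusion criteria list "Alcohol consumption less than 24 hours prior to the study sessions". The plural covers both visits. Participants and Recruitment adds the matching instruction: "Participants will be required to not drink alcohol 24 hours prior to the study session".

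The objective check is described under Procedure. It belongs to the short screening that follows consent on arrival at the first session, "which includes taking measures of weight and breath alcohol concentration (BrAC) (only participants with a BrAC of zero will be enrolled". Zero BrAC is thus a condition of enrolment, which happens once. Table 1 agrees: its minute-0 row reads "Informed consent and screening (session one only", without a counterpart for session two.

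The only other BrAC reading comes after the computerised tasks. The Procedure says "They will then complete questionnaire measures (PANAS, BAES, S-Ang), and a BrAC reading", and Table 1 puts this at minute 65 ("Questionnaire measures (PANAS, BAES, S-Ang), BrAC reading"). The drink is at minute 20 and the tasks start at minute 40.

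**The concern.** Drink is the only factor the study manipulates, and hypotheses H1 to H5 all compare alcohol with placebo. That comparison assumes participants arrive at both visits without alcohol on board. The Protocol thought this worth confirming by instrument at session one, although the abstinence instruction is also in force there. It gives no reason for relying on the instruction alone at session two.

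A zero reading at session one does not carry over. The visits are at least one week apart, and the inclusion criteria select regular drinkers (5 to 35 units a week for women, 10 to 50 for men).

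Two things are at stake. Prior alcohol in a session-two placebo visit makes that visit less of a placebo condition. Prior alcohol in a session-two alcohol visit means the study drink is given on an unverified baseline, which affects the contrast and also bears on participant safety. The check differs by session, so any contamination that goes undetected is tied to session order.

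**Working it through.** **1. Where each reading falls**

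| Step | Session one | Session two |
|---|---|---|
| Exclusion for recent drinking applies | yes | yes |
| BrAC before the drink (screening, minute 0) | yes | none described |
| Drink (minute 20), tasks (from minute 40) | yes | yes |
| BrAC after the tasks (minute 65) | yes | yes |

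The text and Table 1 agree with each other. The mismatch is between both of them and the exclusion criterion.

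**2. How many sessions.** Participants: 88 (Participants and Recruitment). Sessions: 88 × 2 = 176. Session-two visits: 88. Order is counterbalanced with equal numbers (Randomisation), so 88 / 2 = 44 of these are placebo and 44 are alcohol.

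**3. Effect on the pooled difference.** The Protocol gives no contamination rate, so the following are assumptions:
- a share *f* of session-two visits begins with alcohol present, equally in both orders;
- that alcohol alone has the same effect *E* as the study drink, which is a severe case;
- in an alcohol session it adds *aE*, with *a* between 0 (no further effect) and 1 (fully additive).

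The mean alcohol-placebo difference is then:
- placebo-second participants: E(1 − f)
- alcohol-second participants: E(1 + af)
- pooled over equal order groups: E[1 − f(1 − a)/2]

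With a = 1 the shift is zero. With a = 0 the shrinkage is f/2, for example 5% at f = 10%.

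**4. What this means for power.** The Protocol's own figure comes first. A two-sided paired t-test at alpha 0.05 with n = 44 and dz = 0.5 gives power 0.900, so the stated 90% per trait group reproduces (two-sided is assumed; the Protocol does not state it).

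At the unfavourable end (a = 0), dz = 0.5 × (1 − f/2). This keeps the standard deviation of the differences fixed and assumes order is balanced within the trait group:

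| f | dz | power, n = 44 |
|---|---|---|
| 0 | 0.500 | 0.900 |
| 2% | 0.495 | 0.894 |
| 5% | 0.4875 | 0.885 |
| 10% | 0.475 | 0.869 |
| 20% | 0.450 | 0.831 |

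At the other end (a = 1) the mean is unchanged but variance is added. A random participant's difference shifts by −E with probability f/2 and by +E with probability f/2, so the added variance is fE². With the standard deviation set to 1 and E = 0.5, f = 10% adds 0.1 × 0.25 = 0.025, and dz becomes 0.5 / √1.025 = 0.494.

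**5. What the minute-65 reading can do.** In a placebo session a positive value points to alcohol not supplied by the study, but only after the task data are collected. The Protocol attaches no action to it. In an alcohol session a positive value is expected, so it cannot show whether part of it was there on arrival.

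**The case against.** Several counter-arguments have force.

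- **The rule already exists.** Recent drinking is excluded and participants are told to abstain. This stands: what is missing at session two is an objective check before the drink. A verbal question on arrival is neither described nor ruled out.
- **The bias need not go one way.** A reader might infer that residual alcohol simply dilutes the contrast by f/2. The documents do not support that as a general result, because counterbalancing spreads session-two contamination over both drinks, and with additive, equal contamination the pooled shift is zero. The f/2 figure is one end of a range, and the power table above describes that end only.
- **The assumed contamination is severe.** It supposes a full study-drink effect on arrival in people instructed to abstain. Nothing in the Protocol suggests this is common. The main effect of drink also uses all 88 participants, not 44.
- **The late reading helps in part.** It can flag a contaminated placebo session afterwards. Only session-two alcohol visits stay wholly indistinguishable.
- **Zero BrAC is not proof of 24-hour abstinence.** A reader might take session one as fully verifying the exclusion. It does not, and repeating the reading at session two would not either.
- **Safety provisions exist.** The Safety section caps the weight used for dosing at 90 kg, refers to procedures for adverse effects, and offers a place to stay and a taxi. These do not replace a reading before the drink.
- **Analysis handling may sit elsewhere.** How a failing session is treated in the analysis may belong in a statistical analysis plan that is not shown, so its absence is not counted here.

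None of this supplies the missing reading, and no later analysis can recover a value that was never taken.

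**Conclusion.** The point holds as an inconsistency that should be put right. A criterion written for both sessions is checked by instrument before the drink at only one of them, leaving 88 of 176 planned sessions without that check. The documents do not show that contamination will occur, how often, or in which direction the result would move.

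Under the stated assumptions (equal *f* in both orders, prior alcohol as strong as the study drink, *a* between 0 and 1) the pooled difference changes by between nothing and a shrinkage of f/2. At f = 10% that is 0 to 5%, and at the unfavourable end power within a trait group falls from 0.900 to 0.869. If *f* differed between orders the net shift could fall outside this range. Variance rises whenever some visits are contaminated, and the baseline before alcohol is given at session two remains unverified. The statistical effect is modest at small *f*; the case for acting rests on how little the check costs.

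**What to change.** Reconcile Procedure and Table 1 with the Exclusion criteria. Add a BrAC reading on arrival, before the drink, at session two as well as session one, record it, and apply the criterion already stated to both visits. In Table 1 this means separating the arrival reading from the session-one consent and screening row, or adding one line. State that the reading rules out measurable alcohol on arrival and that the 24-hour requirement still depends on participants' compliance.

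The device is already in use. The cost is about a minute per session-two visit, one table line and an occasional rebooked visit.
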